The Alphanumeric Task under the 80% priority condition was one of the primary near transfer outcomes. In this condition, the participants were asked to prioritize one task over the other (e.g., Alphanumeric Equation or the Visual Detection task); therefore, this condition was the closest related to the EmCh approach, and more likely to serve as a transfer measure. The two variables under the 80% priority condition were: 1) *Alphanumeric Task 80% on Detection Task - Total Correct*, and 2) *Alphanumeric Task 80% on Equation Task – Total Correct*. Furthermore, based on a previous model of executive control, we created an Executive Control Composite Score based on measures of working memory (Letter-Number Sequencing total score), cognitive flexibility (WSCT – perseverative responses), inhibitory control (Stroop Color-Word Test-DKEFS Condition 3 – Inhibition, and Condition 4 - Inhibition and Switching), and divided attention (UFOV – Divided Attention Accuracy)⁶⁶. The composite score was created by summing the z-scores of each of the five tests.

Secondary Outcomes: Distant Transfer Outcome

Additional measures were used to assess potential psychosocial changes after the intervention, including the measure of self-efficacy (GSE), engagement in cognitive activities (CLAS), and mood questionnaires targeting symptoms of depression (BDI) and anxiety (BAI).

Acceptability: Post-Intervention Questionnaire

Acceptability was assessed based on participants' quantitative and qualitative responses in the post-intervention questionnaire⁵. Participants were asked to provide scores (0 to 10) and their views on specific aspects of the cognitive training program. For instance, they were asked to provide scores on the difficulty and enjoyability of the game, clarity of instructions, and accessibility of the platform. They were also asked to rate their overall experience in the study. Moreover, participants were asked to answer open-ended questions about the game and its influence on their daily lives.

Statistical Analysis

For the sample size calculation, we considered our previous preliminary data and the flat rule of thumb of at least 30 subjects to estimate a parameter. Therefore, the current sample size ($N=38$) would overcome the sample size from previous similar studies, including 10 young adults, and 15 to 18 older adults per group. The power analysis was conducted with the assumption of 5% attrition between evaluations, having 80% power at $\alpha=0.05$.

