At baseline, the overall sample was described, and comparisons between groups were assessed. The Independent samples T-test was applied for the continuous variables, and chi-squared tests were used for the categorical variables. All outcomes were analyzed following the intent-to-treat principle. To evaluate intervention effects, linear mixed models (LMM) were conducted using the lme4 R package (version 4.5.0). Each model included fixed effects for time (pre vs. post; or session 1 vs. session 12 on the Breakfast Game outcomes), group (experimental vs. control), and the interaction between time and group, with a random intercept for each participant to account for within-subject correlation. Baseline cognitive performance was included as a covariate in all LMM to control for individual variability at baseline. The primary analysis tested time-by-group interactions in the training gains and near-transfer measures, and the secondary analysis examined interactions in the distant transfer measures. Of note, all the Breakfast Game outcomes were based on the trial performance across sessions.

Multiple-comparison corrections across all six outcomes were performed to control the false discovery rate (FDR) using the Benjamini-Hochberg (BH) procedure. Adjusted p-values (q-values) less than 0.05 were considered significant. In addition, effect sizes (Cohen's d) were calculated for the outcome that presented a significant time-by-intervention group interaction. All analyses and visualizations were performed using the R Studio software (version 4.3.1).

Supplementary Material

Figure 1S. CONSORT Check List

CONSORT 2010 checklist of information to include when reporting a randomised trial*			
Section/Topic	Item No	Checklist item	Reported on page No
Title and abstract	1a	Identification as a randomised trial in the title	1
	1b	Structured summary of trial design, methods, results, and conclusions (for specific guidance see CONSORT for abstracts)	2
Introduction			
Background and objectives	2a	Scientific background and explanation of rationale	3-5
	2b	Specific objectives or hypotheses	5
Methods			
Trial design	3a	Description of trial design (such as parallel, factorial) including allocation ratio	5-6
	3b	Important changes to methods after trial commencement (such as eligibility criteria), with reasons	NA
Participants	4a	Eligibility criteria for participants	6-7
	4b	Settings and locations where the data were collected	6-7

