	17a	For each primary and secondary outcome, results for each group, and the estimated effect size and its precision (such as 95% confidence interval)	16-19; Tables 2 & 3
Outcomes and estimation	17b	For binary outcomes, presentation of both absolute and relative effect sizes is recommended	NA
Ancillary analyses	18	Results of any other analyses performed, including subgroup analyses and adjusted analyses, distinguishing pre-specified from exploratory	18
	19	All important harms or unintended effects in each group (for specific guidance see CONSORT for harms)	NA
Harms			
Discussion			
Limitations	20	Trial limitations, addressing sources of potential bias, imprecision, and, if relevant, multiplicity of analyses	21
Generalisability	21	Generalisability (external validity, applicability) of the trial findings	19-20
Interpretation	22	Interpretation consistent with results, balancing benefits and harms, and considering other relevant evidence	19-21
Other information			
Registration	23	Registration number and name of trial registry	6
Protocol	24	Where the full trial protocol can be accessed, if available	6; Supplementary Material
Funding	25	Sources of funding and other support (such as supply of drugs), role of funders	22

*We strongly recommend reading this statement in conjunction with the CONSORT 2010 Explanation and Elaboration for important clarifications on all the items. If relevant, we also recommend reading CONSORT extensions for cluster randomised trials, non-inferiority and equivalence trials, non-pharmacological treatments, herbal interventions, and pragmatic trials. Additional extensions are forthcoming: for those and for up to date references relevant to this checklist, see www.consort-statement.org.

CONSORT 2010 checklist

Page 2

Figure 2S. Intervention Protocol Details

Session Number	Intervention Phase	Level of Supervision	Trials Structure	Duration	Session Structure	Tasks Presentation	Cooking Task	Table Setting Task Rules	EmCh Instructions (Experimental Group only)
1	Mock Session: Instruction and practice	Supervised	Instructions + practice 8 trials of 4.5 min each	1h20 min	Full Game: Both Tasks	Same screen/ Split screen	2-5 foods: Gradual Progression	By Tableware or Guest (random)	No
2	Intervention Session 1: (Baseline Pre EmCh)	Supervised	8 trials of 4.5 min each	45 min	Full Game: Both Tasks	Split screen	5 foods	By Tableware or Guest (random)	No

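### Cohen's d is planned only for outcomes with a significant interaction, and no confidence interval is planned, so reported d values are too large on average and do not fit checklist item 17a

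*Combined protocol and SAP*

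**What the plan says.** The Statistical Analysis section fits a linear mixed model with a time-by-group term to each outcome and applies a Benjamini-Hochberg correction across six outcomes. Six is also the count of primary outcomes: three game scores, two Alphanumeric scores and the executive control composite. The decision rule is: "Adjusted p-values (q-values) less than 0.05 were considered significant". Cohen's d values then "were calculated for the outcome that presented a significant time-by-intervention group interaction". The section does not say which standard deviation forms the denominator of d, and it mentions no confidence interval for any outcome.

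The CONSORT checklist in the Supplementary Material (Figure 1S), item 17a, covers each primary and secondary outcome. It lists results by group with "the estimated effect size and its precision (such as 95% confidence interval" and points to pages 16-19 and Tables 2 and 3. Those tables are not part of the documents.

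On sample size, the section says "we considered our previous preliminary data and the flat rule of thumb of at least 30 subjects to estimate a parameter". It also states: "The power analysis was conducted with the assumption of 5% attrition between evaluations, having 80% power at" an alpha of 0.05. It gives no effect size, standard deviation or test.

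**The concern.** If an estimate is reported only after its test succeeds, the reported estimates are a selected set. In a small trial a modest true effect reaches significance only when chance has pushed the estimate well above it, so the average reported d exceeds the true d. Outcomes that miss the threshold get no planned standardised effect and no planned interval, so a reader cannot see which effects remain plausible for them.

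This matters because the trial is a stage 1B pilot, and its sample size is justified partly by a rule of thumb for estimating a parameter. If a later trial were sized on a d selected in this way, it could be too small.

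The trigger is also unclear for the four distant-transfer outcomes (GSE, CLAS, BDI, BAI). They appear to lie outside the six-outcome correction, so the text does not settle whether a q-value or an unadjusted p-value decides if they receive a d.

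**Working it through.** **Inputs.** N = 38, 1:1 allocation, 5% attrition, alpha 0.05, 80% power and BH over six outcomes come from the documents. Three inputs are assumptions: a two-sided test; 38 as the total, because it is said that it "would overcome the sample size from previous similar studies, including 10 young adults, and 15 to 18 older adults per group"; and the true effect, which is not stated and is therefore varied. Evaluable: 38 × 0.95 = 36.1, so about 18 per arm.

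**The plan's own figure.** The 80% power cannot be reproduced without an effect size. Solved backwards, d = (1.96 + 0.842) × √(2/18) = 0.93 (0.96 with the t distribution). With 19 per arm it is 0.91 (0.93). If 38 were per arm, it would be about 0.64 to 0.65.

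**Smallest d that can be significant**, with a two-sample t-test on the between-group difference in change and d in units of the SD of change:
- at p<0.05: t(0.975, 34) × √(2/18) = 2.032 × 0.333 = 0.68;
- at 0.05/6: 2.802 × 0.333 = 0.93. This is the strictest BH case, when only one outcome qualifies. The bar relaxes as more do.

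**Inflation given significance.** Simulated with 18 per arm. The BH columns assume six independent outcomes with the same true d.

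| True d | Chance p<0.05 | Mean reported d, p<0.05 | Ratio | Ratio, BH over six | Chance that no outcome gets a d, BH |
|---|---|---|---|---|---|
| 0.2 | 9% | 0.85 | 4.2 | 5.3 | 88% |
| 0.3 | 14% | 0.86 | 2.9 | 3.5 | 79% |
| 0.4 | 21.5% | 0.88 | 2.2 | not run | not run |
| 0.5 | 31% | 0.91 | 1.8 | 2.1 | 46% |
| 0.8 | 65% | 1.02 | 1.28 | 1.33 | 5% |
| 0.94 | 78% | 1.09 | 1.16 | 1.18 | under 1% |
| 1.2 | 94% | 1.27 | 1.06 | 1.06 | about 0% |

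The table averages the absolute value of d, except that the 0.4 row averages signed d; the ratio rounds to 2.2 either way. If 38 were per arm, the p<0.05 ratios would be 2.9 at 0.2, 1.33 at 0.5 and 1.05 at 0.8.

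**Without the selection.** When d is reported for every outcome, its mean at 18 per arm is 0.20, 0.51, 0.82 and 0.96 for true values of 0.2, 0.5, 0.8 and 0.94, which is close to the truth. The 95% CI half-width is about 0.66 to 0.68.

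**Change of standardiser.** If d is divided by the baseline SD, the SD of change is √(2(1 − ρ)) baseline SDs, where ρ is the pre-post correlation (not in the documents):
- ρ = 0.7: √0.6 = 0.775, threshold 0.677 × 0.775 = 0.52, mean reported d at true 0.4 about 0.68, ratio 0.68/0.4 = 1.7;
- ρ = 0.8: √0.4 = 0.632, threshold 0.677 × 0.632 = 0.43, mean about 0.58, ratio 0.58/0.4 = 1.45.

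**What this would mean for a later trial.** Required sample size varies as 1/d². A trial sized on the reported d would have this fraction of the sample it needs at true 0.4: (0.4/0.88)² = 0.21 on the change-SD scale, or (0.4/0.68)² = 0.35 to (0.4/0.58)² = 0.48 on the baseline-SD scale. At true 0.94 it would be (1/1.16)² = 0.74.

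**The case against.** A reader might infer that the trial will report only inflated effects, and nothing for the other outcomes. The documents support neither.

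- **Nothing for the rest.** The mixed model is fitted to every outcome, so an interaction estimate and standard error exist for each. The sentence restricts only Cohen's d and does not say that other estimates are withheld. Item 17a says effect size and precision are reported throughout, and Tables 2 and 3 cannot be checked. What stands is that the analysis text commits to no interval and to no standardised effect for non-significant outcomes. It also uses the term effect size to mean Cohen's d, which is why 17a needs reconciling.
- **Only inflated.** Inflation is a property of the average. At a true d of 0.8 about 21% of estimates significant at p<0.05 lie below the truth, and at 0.94 about 35% do. If the true effect is near the 0.93 to 0.96 implied by the claimed power, inflation is modest. This stands, but the documents give no effect size that would let the sponsor rely on so large an effect.
- **Fixed thresholds.** The 0.68 bar is not a property of the planned model, which has a baseline covariate and a random intercept. The game outcomes are also said to rest on trial performance across sessions, which could move their threshold again. This stands too: the ratios are illustrative, though the direction does not depend on them.
- **Harm to a later trial.** No passage says that a later trial will be sized on the reported d, so this consequence is conditional.

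**Conclusion.** The point holds in a limited form. The written rule makes a standardised effect conditional on significance and plans no interval, so the reported d values overestimate on average and non-significant outcomes have no planned d. The text and item 17a do not fit unless 17a refers to unstandardised estimates.

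The size depends on unknowns. Under the two-sample approximation at p<0.05 with about 18 per arm, inflation runs from about 4.2 times at a true d of 0.2 to 1.16 times at 0.94. It is about 1.4 to 1.7 times at a true 0.4 on the baseline-SD scale with correlation 0.7 to 0.8. These figures rest on 38 being the total, a two-sided test and a simplified stand-in for the mixed model. The hypothesis tests themselves are unaffected. The change should be made because it removes a selection at almost no cost.

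**What to change.** Replace the effect-size sentence in the Statistical Analysis section. For all six primary and four secondary outcomes, whatever the p-value, report:
- the model-based time-by-group estimate with its 95% CI;
- a standardised effect with its 95% CI, naming the denominator (for example the pooled baseline SD).

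Then state what item 17a and Tables 2 and 3 contain, so that the checklist and the analysis text agree. With every outcome reported, no significance trigger is needed for the distant-transfer measures.

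The cost is one edited sentence and a few table columns. No new data, participants or change to N is needed, and the interaction estimates come from models already planned.
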